#### 6.4 Analysis

#### Primary endpoint

Analysis of the bowel function component of the Modified Inflammatory Bowel Disease questionnaire is the primary endpoint, and analysis will be carried out on an intention to treat basis. The mean difference in change from baseline to 12 months in both trial arms will be compared using the Mann-Whitney U test, or unpaired t-test if the values are approximately normally distributed. If necessary, multivariate analysis will be used to adjust for any potential confounding factors, though the ability to use multivariate analysis will be limited by the fact there are only 33 patients in one arm. The impact of missing values will be investigated by using techniques such as LOCF.

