# 5.3 Allocation of treatment

Treatment allocation will be in a 2:1 ratio of Tocovid SupraBio+PTX treatment: matched placebo and will be based on computer generated random permuted blocks. Patients will be asked to start their allocated treatment the day after randomisation. Pharmacy will be informed of the randomisation and hold records in the pharmacy file.

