# 6 STATISTICAL CONSIDERATIONS

# 6.1 Stratification

Patients will be stratified according to:

- i) the severity of their symptoms (IBDQ-B  $\geq$ 60 vs. IBDQ-B <60)
- ii) average daily fat intake ≥90g fat/day vs. intake <90g fat/day

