#### Primary endpoint

We have previously shown that the IBDQ-B (Inflammatory Bowel Disease Questionnaire is a more sensitive tool than the more commonly used RTOG (Radiation Therapy Oncology Group) and LENT SOM scoring tool (20). It is a questionnaire developed and validated for patients with chronic inflammatory bowel disease, in whom changes in score associated with improved, stable or worsening symptoms have been reported (95). The whole questionnaire is scored out of 224 and gives a bowel health and overall quality of life score. The bowel subset of the IBDQ is scored out of 70, using data from 10 of the 32 questions. Mean (±SD) changes in IBD guestionnaire bowel subset score were 15 ±10 for n=109 with improving symptoms,  $3 \pm 7$  for n=63 with stable symptoms and -3 ±6 for n=8 with worsening symptoms. In the PPALM trial, 10 will be used an estimate of the standard deviation (SD) of the change at 12 months. A difference in guestionnaire score of 7.5 is selected as representing a clinically worthwhile improvement in response to 12 months of Tocovid SupraBio+PTX compared to placebo. We therefore need 99 patients (66 GT3+PTX:33 placebo) for 85% power employing a two-sided 1.67% significance level. We have adopted this level of significance because we wish to keep a 5% overall false positive rate after inclusion of the secondary endpoints relating to changes in bleeding and faecal incontinence.

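### The primary analysis in section 6.4 is an unadjusted two-sample test chosen from the observed distribution; one predefined model adjusted for baseline IBDQ-B and fat intake would be more precise at no cost

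*Protocol*

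**What the plan says.** Under the primary endpoint heading of section 6.4, the protocol states that the mean difference in change from baseline to 12 months "will be compared using the Mann-Whitney U test, or unpaired t-test if the values are approximately normally distributed". It gives no rule for judging normality.

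On covariates, the same paragraph says: "If necessary, multivariate analysis will be used to adjust for any potential confounding factors". It names no factors, and adds that such modelling is limited because one arm has only 33 patients.

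Section 6.1 begins "Patients will be stratified according to" and lists two factors: IBDQ-B at or above 60 against below 60, and fat intake at or above 90 g per day against below 90 g. Section 5.2 requires both at randomisation. Neither appears in the primary test.

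The sample size in section 6.3 rests on an unadjusted comparison of changes. For the effect, "7.5 is selected as representing a clinically worthwhile improvement"; for the spread, "10 will be used an estimate of the standard deviation (SD) of the change at 12 months". The result is "We therefore need 99 patients (66 GT3+PTX:33 placebo) for 85% power", "employing a two-sided 1.67% significance level".

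**The concern.** Three features of the paragraph sit badly together.

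- **The test depends on the data.** Mann-Whitney or t-test is decided from the observed distribution, and so is whether to adjust. The two tests also target different things. Section 6.3 sizes the trial on a 7.5-point difference in means, which a Mann-Whitney test does not estimate.
- **The design uses information that the analysis discards.** Stratifying on baseline IBDQ-B and fat intake implies that they are expected to matter. If they predict outcome, leaving them out makes the standard error larger than it need be. Baseline very likely predicts change here: the bowel subset is scored out of 70, so a patient who starts at 60 or more can gain at most 10 points.
- **The reason given against adjustment is weak.** The size of the smaller arm would matter for a long covariate list, but not for two covariates.

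At stake are the precision of the primary result and having one predefined answer to report.

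**Working it through.** **Inputs.** From section 6.3: difference 7.5, SD of change 10, two-sided alpha 0.0167, power 85%, 66:33 evaluable. From section 5.3: "Treatment allocation will be in a 2:1 ratio of Tocovid SupraBio+PTX treatment: matched placebo". Not in the protocol: the correlation rho between baseline and 12-month IBDQ-B. I take 0.3 to 0.9, with equal variances at the two times.

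**Step 1: reproduce the plan's figure.**

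The normal approximation for the placebo arm at 2:1 is

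n = 1.5 × [10 × (2.393 + 1.036) / 7.5]² = 31.4, rounded to 32, or 96 in total.

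For the exact t-test, the standard error is 10 × √(1/66 + 1/33) = 2.132 and the noncentrality is 7.5 / 2.132 = 3.518. Power is 84.6% at 64:32 and 85.8% at 66:33. So 33 is the smallest placebo arm that reaches 85%, for a total of 99.

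The Mann-Whitney route (relative efficiency 0.955 under normality) gives 31.37 / 0.955 = 32.8, rounded to 33, again 99. For drop-out, 99 / 0.85 = 116.5, rounded to 117.

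Both stated figures reproduce, so the unadjusted test has the planned power.

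**Step 2: add baseline.**

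With equal variances s² at both times, the variance of change is 2s²(1 − rho). The ANCOVA residual variance is s²(1 − rho²). Their ratio is (1 + rho)/2, so with the SD of change held at 10 the residual SD is 10 × √((1 + rho)/2).

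| rho (assumed) | Residual SD | Power at 66:33 | Total N for 85% power |
|---|---|---|---|
| unadjusted | 10.00 | 85.8% | 96 |
| 0.3 | 8.06 | 97.2% | 63 |
| 0.5 | 8.66 | 94.6% | 72 |
| 0.7 | 9.22 | 91.4% | 81 |
| 0.9 | 9.75 | 87.7% | 90 |

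Power is from the noncentral t with one degree of freedom spent on the covariate. Total N uses the normal approximation, so it compares with 96 and not with 99.

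The gain can also be framed without rho. If the covariates together explain 5%, 10% or 20% of the variance of the change, power is 87.7%, 89.6% or 93.1%.

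**Step 3: can 99 patients carry the model?**

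Intercept, treatment, baseline IBDQ-B and fat stratum are 4 parameters, leaving 95 residual degrees of freedom. Going from 96 to 95 for the fat stratum costs about 0.01 percentage points of power (94.61% to 94.60% at rho 0.5).

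**Step 4: does the choice of test harm the error rate?**

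I simulated 20,000 trials per setting at 66:33. The rule was an assumed Shapiro test at 5% on the residuals, then t-test or Mann-Whitney.

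| No true effect, nominal 1.67% | Fixed pretest | Smaller of the two p-values |
|---|---|---|
| Normal data | 1.54% | 1.8% |
| Skewed (gamma) data | 1.61% | 2.2% |

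A fixed rule is harmless. With no rule, the smaller p-value could be taken, and the excess is then modest. This covers the choice of test only, not optional adjustment.

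**The case against.** The strongest reply is that the plan is already sound. The trial was sized for an unadjusted comparison of changes and reaches its 85%. Baseline is not ignored, since it enters by subtraction. Leaving stratification factors out makes a test conservative, not liberal. On this view, preferring ANCOVA in a phase II trial is a choice between acceptable analyses, and an SAP that is not shown may settle the normality rule and the covariates.

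Most of that stands, and it rules out four stronger readings that a reader might infer.

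- **That power already bought is thrown away.** It is not. The 99 patients were bought for the unadjusted test, which delivers 85.8%. Adjustment would add to that.
- **That the Mann-Whitney branch falls short of 85%.** Simulation does give about 83.5% to 83.8%, but with normal data, which section 6.4 sends to the t-test. In the skewed case Mann-Whitney had 92.8% against 85.5% for the t-test.
- **That the switch inflates the false-positive rate.** Under a fixed pretest it does not (step 4).
- **That chance baseline imbalance is a serious threat.** Stratifying at 60 limits it at the very point where the ceiling bites. Only imbalance within strata remains.

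The appeal to an unseen SAP does not remove the point. The protocol itself fixes an unadjusted default and gives a reason against adjusting, and both can be judged as written.

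**Conclusion.** The point holds as a matter of efficiency and of fixing one answer in advance. The primary analysis is valid and adequately powered on the protocol's own inputs.

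The forgone gain is about 2 percentage points of power if rho is 0.9, 6 at 0.7, 9 at 0.5 and 11 at 0.3. Equivalently, 5% to 35% of the variance could be removed. These sizes rest on an assumed rho, on equal variances at both times and on a linear relation with baseline. The cap at 70 may strain the last two, so the exact gain is uncertain. The direction is the same throughout the range examined.

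Separately, the protocol does not commit to one estimate of the 7.5-point mean difference that it was sized to detect. Its argument from 33 patients in one arm does not justify leaving two covariates out.

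**What to change.** In section 6.4, and in the SAP if there is one:

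- Name one primary analysis: an ANCOVA of 12-month IBDQ-B on treatment, continuous baseline IBDQ-B and fat-intake stratum. Report the adjusted mean difference with its 98.33% interval, matching the planned two-sided 1.67%.
- Keep one rank test stratified by the randomisation factors (van Elteren) as a prespecified sensitivity analysis, which also covers marked skewness.
- Delete the normality-based switch, the conditional adjustment and the remark about 33 patients.

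The sample size can stay at 99 evaluable and 117 recruited; the extra precision is then a margin. The cost is wording only, because both covariates are already required before randomisation. The change should be made before unblinded outcome data are seen.

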#### Secondary Endpoints

The proportions of patients showing a change in rectal IBDQ bleeding score and Faecal incontinence score will be compared using Fisher's exact test.

There will be no formal statistical analysis of the other secondary endpoints but the descriptive nature of these results will be used to strengthen the interpretation of changes in the primary endpoint. Several analyses will be carried out including but not limited to the following:

- i) Changes in modified CTCAE Version 4 grades.
- ii) Standard procedures will be followed for describing quantitative changes in QoL domains using EORTC Quality of Life Questionnaires (QLQ-C30 and CR29).
- iii) Photographs of rectal mucosa will be scored by two experienced endoscopists, who will be blinded with respect to treatment allocation and time of assessment (pre- or post-treatment). The mucosal appearance will be scored using the Wachter classification (51). Disagreement in any scores will be resolved by arbitration after discussion with a third independent endoscopist. Differences in the appearance before and after treatment between the two groups will be assessed.
- iv) Change in levels of 3 serum markers of fibrosis.

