#### 6.2.2 Secondary endpoints

- i) Change at 12 months in rectal IBDQ bleeding score between the two groups in those patients presenting with grade 2, 3 or 4 bleeding.
- ii) Change at 12 months in IBDQ faecal incontinence score between the two groups in those patients presenting with grade 1 or greater incontinence.
- iii) Proportion of items graded as marked or severe (grade 3 or 4).
- iv) Physician assessment of rectal dysfunction using the modified CTCAE Version 4 grading.
- v) Patient self-assessments: QLQ–C30 and CR29 and the Gastrointestinal Symptom Rating Scale.
- vi) Photographic assessments of rectal mucosa.
- vii) Serum fibrosis marker levels.

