#### Secondary endpoints

We estimate that 40% of patients will have grade 2, 3 or 4 bleeding, based on our ongoing trial evaluating hyperbaric oxygen in a comparable group of patients, comprising 39 of the 99 patients. The reduction in bleeding in this group of patients will be compared between randomised groups. A reduction in the true proportion of patients showing a fall in their grade of rectal bleeding at 12 months from 70% showing a fall (i.e. 7 in 10) in the Tocovid SupraBio+PTX group to 10% in the placebo group would be detectable (80% power, 1.67% two sided significance level). The pattern of rectal bleeding change in the patients with grade 0-1 bleeding at baseline will be reported but not formally compared between arms. This group is of less interest because mild bleeding does not represent a major impediment to daily living and these individuals are very unlikely to develop serious rectal bleeding over the period of the trial.

We expect that 70% of patients will have grade 1 (35%) or 2 (35%) faecal incontinence, based on the same trial evaluating hyperbaric oxygen, comprising 69 of the 99 patients, and this subgroup can be used to examine the reduction in incontinence. A reduction in the true proportion of patients showing a fall in their grade of faecal incontinence at 12 months from 55% in the Tocovid SupraBio+PTX group to 10% in the placebo group would be detectable (80% power, 1.67% two sided significance level). The pattern of faecal incontinence change in the patients who are grade 0 at baseline will be reported but not formally compared between arms.

The combined false positive rate for the three endpoints described above is 5% (3 x 1.67%).

Our aim is 99 evaluable patients, and 117 patients will therefore be recruited to allow for a 15% drop out rate.

23

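### The bleeding and faecal incontinence endpoints, each tested at 1.67%, are defined on one scale, powered on another, and tested with no stated direction of change

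*Protocol*

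**What the plan says.** Three endpoints share the 5% false-positive rate: the primary and two secondary endpoints, each at a two-sided 1.67% (section 6.3). The two secondary endpoints are described as follows.

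- **Definition** (Summary, 5.7.2 and 6.2.2, same content). Bleeding: "Change at 12 months in rectal IBDQ bleeding score between the two groups in those patients presenting with grade 2, 3 or 4 bleeding". Incontinence: "Change at 12 months in IBDQ faecal incontinence score between the two groups in those patients presenting with grade 1 or greater incontinence". The outcome is an IBDQ score; grade only selects the subgroup.
- **Power** (6.3, Secondary endpoints). The outcome is a responder proportion on grade: "A reduction in the true proportion of patients showing a fall in their grade of rectal bleeding at 12 months", 70% on active against 10% on placebo. Incontinence is treated in the same way, at 55% against 10%. Each contrast is said to be detectable with 80% power.
- **Test** (6.4, Secondary Endpoints). "The proportions of patients showing a change in rectal IBDQ bleeding score and Faecal incontinence score will be compared" using Fisher's exact test. No direction or threshold is given, and the baseline-grade restriction is not repeated. The same section puts changes in modified CTCAE grade among the results that get no formal analysis.

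**The concern.** These are two of the three formal tests, and the primary endpoint's significance level was lowered to make room for them. The outcome that was powered (fall in grade) is left descriptive in 6.4, and the outcome that is tested (change in IBDQ score) has no power calculation.

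The wording in 6.4 also sets no direction. Applied as written, deterioration is an event. A real benefit could be cancelled by worsening on placebo, and a significant difference in the proportion changed need not be a benefit. If instrument, direction and cut-point stay open, they could also be chosen after the data are seen.

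**Working it through.** **1. The passages side by side**

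| Section | Instrument | Summary | Direction | Baseline-grade subgroup |
|---|---|---|---|---|
| Summary, 5.7.2, 6.2.2 | IBDQ score | change at 12 months | not stated | stated |
| 6.3 | grade | proportion of patients | fall (improvement) | stated |
| 6.4 | IBDQ score | proportion of patients | not stated | not stated |

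Section 6.3 does not name the grading scale. The only graded bleeding and incontinence scales shown are in the modified CTCAE (Appendix 4), so that is an inference. The two instruments measure different things. Appendix 1 asks patients how often they have bleeding or soiling, in seven categories. Appendix 4 grades incontinence by pad use and need for surgery, and bleeding mainly by the intervention needed.

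They also run in opposite directions. In 6.3, improving patients have a mean IBDQ bowel-subset change of +15 and worsening patients −3, so a rise is improvement. In Appendix 4, 0 is no symptoms, so a fall is improvement. Carrying the word *fall* from 6.3 over to the IBDQ score would count worsening as response.

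**2. Inputs for the power check**

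- Two-sided alpha 0.0167 (6.3); allocation 2:1 (5.3).
- Bleeding subgroup 39 of 99, split 26:13. Incontinence subgroup 69 of 99, split 46:23 (6.3).
- Improvement rates: 70% vs 10% (bleeding) and 55% vs 10% (incontinence), from 6.3.
- Worsening rates: none in the protocol; every value below is an assumption.

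Power = Σ P(X = i)·P(Y = j) over all tables with Fisher two-sided p ≤ 0.0167, where X and Y are independent binomial counts in the active and placebo arms.

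**3. The plan's own figure**

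For the directional outcome in 6.3, the stated power is 80%. Exact Fisher power is 90.4% (bleeding) and 92.7% (incontinence); the normal approximation gives 94.3% and 94.1%. The 80% is not reproduced, but it errs on the cautious side and is a separate matter.

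**4. The literal rule in 6.4**

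P(any change) = P(improve) + P(worsen). For example, with 5% worsening on active and 20% on placebo, bleeding becomes 70% + 5% = 75% vs 10% + 20% = 30%, and incontinence 55% + 5% = 60% vs 30%.

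| Assumed worsening, active / placebo | Bleeding, any change | Power | Incontinence, any change | Power |
|---|---|---|---|---|
| 0% / 0% (same as testing improvement) | 70% vs 10% | 90% | 55% vs 10% | 93% |
| 10% / 10% | 80% vs 20% | 89% | 65% vs 20% | 87% |
| 5% / 10% | 75% vs 20% | 80% | 60% vs 20% | 77% |
| 5% / 20% | 75% vs 30% | 57% | 60% vs 30% | 42% |
| 10% / 30% | 80% vs 40% | 48% | 65% vs 40% | 26% |

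**5. Two constructed tables**

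- Active: 18 of 26 change, all improved. Placebo: 9 of 13 change, 1 improved and 8 worsened. On any change, 18/26 vs 9/13 gives p = 1.00. On improvement, 18/26 vs 1/13 gives p = 0.0004.
- Conversely, 20/26 vs 3/13 changed gives p = 0.002, even if every change on active were a worsening.

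**The case against.** The strongest reply is that 6.4 should not be read alone. Section 6.3 speaks of a reduction in bleeding and incontinence and counts patients whose grade falls, so *change* in 6.4 is probably loose wording for improvement. That stands. A reader might infer that the sponsor means to count worsening as success; the protocol does not support this. It also stands that 6.2.2 and 6.4 share an instrument, so the firm conflict is between IBDQ score and grade, with the missing direction added to it.

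A reader might also infer that power must collapse. That needs much more worsening on placebo than on active, and no rates are given. The introduction (1.2) calls most chronic radiation syndromes progressive, but the same sentence says some symptoms may improve, and it sets no 12-month rate for a single item. The only worsening count in the protocol, in 6.3, is 8 of 109 + 63 + 8 = 180 patients with a different disease.

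Nor is Fisher's test itself at fault. On improvement, at the plan's own rates, it exceeds the stated 80%. A rank test on the item change is a legitimate alternative, but that is a preference.

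An exact responder threshold may reasonably be left to the SAP. What the reply does not remove is that the protocol names two instruments for the same formal tests. An SAP that picks one must contradict some section of the protocol, and *fall* cannot be moved across scales that point in opposite directions.

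**Conclusion.** The point holds as an inconsistency in the current text that should be fixed. Two endpoints carrying 1.67% each are defined on the IBDQ score, powered on a fall in grade, and tested on an undirected change in IBDQ score. The stated power does not describe the test in 6.4, and that rule, followed literally, can give a wrong answer.

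The size of the harm is uncertain. Relative to 90% and 93% for improvement, the literal rule costs 1 to 6 percentage points if 10% worsen in both arms, and much more if worsening is concentrated on placebo (57% and 42% at 5% vs 20%; 48% and 26% at 10% vs 30%). These figures take the plan's improvement rates and subgroup sizes as given and assume the worsening rates.

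The definition and test of the primary endpoint, its significance level and the total of 99 evaluable patients are not affected.

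**What to change.** - Choose one instrument for each endpoint and one directional definition: improvement, with its threshold, at 12 months in the stated baseline-grade subgroup. If the IBDQ item is chosen, say that improvement is a rise in score.
- Use that definition identically in the Summary, 5.7.2, 6.2.2, 6.3 and 6.4. In 6.4, replace *a change* with *an improvement* and restate the subgroup.
- Keep Fisher's exact test on improvement if a responder comparison is wanted. A rank test on the change in the item score is optional.
- Restate the power in 6.3 for the chosen outcome. The present 70% vs 10% and 55% vs 10% refer to grade and would need a new justification on the IBDQ item.

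The cost is a wording amendment and one recalculated power statement. No new data or visits are needed.

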#### 6.5 Frequency of analyses

There will be a sequential monitoring of toxicity, and the first analysis will be carried out when the first 21 patients have completed the first 12 months of assessment. Toxicity and the frequency and nature of adverse events will be compared between the randomised groups. Summary measures and non-parametric tests will be used as necessary. In particular, the proportion of patients experiencing toxicity grade 3 or 4 and the maximum toxicity grade will be compared. An analysis of safety endpoints by treatment received will be performed.

# 7 RESEARCH GOVERNANCE

#### 7.1 Trial Administration and Logistics

The Royal Marsden NHS Foundation Trust is the agreed Sponsor of this study in accordance with the Medicines for Human Use (Clinical Trials) Regulation 2004 as amended and in line with the Research Governance Framework for Health and Social Care and the principles of Good Clinical Practice (GCP).

#### 7.1.1 Chief Investigator responsibilities

The Chief Investigator has overall responsibility for facilitating and coordinating the conduct of the trial.

24

CCR3894 Randomised double-blind controlled phase II trial of gamma-Tocovid SupraBio in combination with pentoxifylline in patients suffering long-term adverse effects of radiotherapy for pelvic cancer.

